6 HANDLING OF DROPOUTS AND MISSING DATA

6.1 Missing Information for Adverse Event

For subjects with the missing information for adverse events, the following imputation rules will be applied:

- An adverse event with onset date equivalent to the first dosing date will be considered to be treatment-emergent unless there is evidence to conclude that it is not.
- An adverse event with missing severity will be assigned to the highest severity observed for the subject, among all events with the same preferred term; if there are no other AEs with same preferred term and non-missing severity, the adverse event will be counted as severe.
- An adverse event with missing relationship to study drug will be assigned to possible relationship (i.e. related).

6.2 Missing Dates or Partially Missing Dates

Missing or partially missing dates will be imputed for concomitant medications, procedures and adverse events (AEs). Specific rules for handling missing or partially missing dates are provided in the Appendix C.

7 STATISTICAL METHODOLOGY AND STATISTICAL ANALYSES

7.1 General Considerations and Statistical Methods

For continuous variables, descriptive statistics will include the number of subjects, mean, standard deviation (SD), standard error (SE), median, 25th, 75th percentiles, minimum and maximum.

For categorical variables, descriptive statistics will include frequencies and percentages in each category.

When mean change from baseline is assessed, a subject will be included in the analysis if he/she has a baseline and a post-baseline measurement.

All statistical tests will be conducted at a two-sided alpha level of 0.05 and 95% confidence intervals will be utilized, unless otherwise stated.

All table results, unless otherwise specified, will be displayed by age cohort, starting dose, and overall. For subjects who transition to maintenance hemodialysis or peritoneal dialysis during the study, their data after the start of dialysis will be excluded from summary tables and will be included in listings only.

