4.3 Subject Withdrawal

Within the provisions of informed consent and assent (if required) and good clinical judgment with respect to the subject's safety, every attempt should be made to have subjects complete both Treatment Periods and Follow-up Period. Subjects and subject's legally authorized representatives will be informed that they are free to withdraw from the study at any time. The Investigator and/or the Medical Monitor may exercise his or her medical judgment to terminate a subject's participation in the study because of clinically significant changes in any clinical or laboratory parameter. If the Investigator is concerned regarding any potassium value, a re-test of potassium level and/or ECG evaluation for electrophysiological consequences can be initiated by the Investigator at his/her discretion.

On an ongoing basis, the investigator will monitor the degree of burden of participation in the study as well as the associated risk. Participation in this study should only be continued if the investigator determines there is no more than a minimal increase over the burden and risk that are described in the protocol or associated with routine clinical examinations, clinical care and treatment of patients with chronic kidney disease and hyperkalemia.

All subjects withdrawn early from the study for any reason will be followed for safety for 2 weeks after receiving the last dose of patiomer. Subjects who meet any of the following criteria at any time during the study must be withdrawn from the study and should be medically managed as per standard of care by the Investigator:

- Serum magnesium < 1.0 mg/dL (< 0.41 mmol/L) confirmed by re-test
- Potassium-related ECG changes
- Treatment-related SAE (SAE form must be completed)
- Pregnancy (pregnancy form must be completed)
- Withdrawal of assent by subject (if required) or informed consent by legally authorized representative

Other reasons for withdrawal may include:

- Adverse Event
- Protocol deviation
- Subject's non-compliance: poor compliance with study treatment

- Investigator's decision (e.g., in the Investigator's judgment discontinuation is in the subject's best interest; e.g., need for prohibited medication)
- Subject is lost to follow-up: the subject did not return for visits and study personnel were unable to contact the subject
- Subject transitions to dialysis during the study and does not require additional patiromer treatment (see Section 4.4 for details)

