4.4 Dialysis

The medical monitor should be contacted prior to enrolling a subject if it is anticipated that subject will transition to dialysis any time during the study. In addition, the medical monitor should be consulted when the investigator determines that an enrolled subject will require dialysis. Patients who are anticipated to require dialysis shortly after enrollment (within 6-8 weeks of Day 1) may not be suitable for enrollment due to unstable medical status and fluctuating potassium levels. In most cases for subjects who transition to maintenance hemodialysis or peritoneal dialysis during the study patiromer should be discontinued as soon as feasible. Continuation of patiromer (including a dose of 0 g/day) may be allowed for patients transitioning to dialysis under the following conditions:

- The Investigator determines continuation of patiromer may be needed to control hyperkalemia; (documentation of medical justification must be provided)

- Agreement to follow additional guidance for potassium monitoring (to be provided as needed)
- Approval by the medical monitor

Alternative strategies to control hyperkalemia (e.g., adherence to low potassium diet, dialysis prescription) should be utilized to facilitate withdrawal of patiromer and management of hyperkalemia once patiromer is discontinued.

Dialysis sessions conducted during the study should be documented in eCRF. Subjects who undergo dialysis and discontinue patiromer should be withdrawn from the study. Subjects on a patiromer dose of 0 g/day should be withdrawn from the study once the investigator determines patiromer will no longer be required. Any subject discontinuing the study early should complete the Early Termination visit (see Section 6.4) and the follow up visits.

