8.2 Procedures for Eliciting, Recording and Reporting Adverse Events

8.2.1 Adverse Event Reporting Period

AEs, including SAEs, will be collected throughout the study period, beginning from the time the ICF is signed until the subject's last study visit (normally the last follow-up visit). Any AE or SAE will be followed until it resolves or becomes stable. The Investigator must report any AEs that occur after the protocol specified reporting period if according to the Investigator's assessment there was a reasonable possibility that the AE was related to patiromer or any study procedures.

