9.2 General Considerations

Tables and listings will present results by age cohort and starting dose and will include demography, subject disposition, baseline disease characteristics and other medical history, and concomitant medications. Efficacy variables and analyses are discussed in Section 9.4. Safety variables and analyses are discussed in Section 9.5.

All analyses of potassium levels will use central laboratory values. The potassium values obtained locally and used to manage subjects' dose levels at study sites, may also be used in estimating missing central laboratory values.

The efficacy and safety populations will include all subjects who have taken at least one dose of patiomer. For subjects who transition to maintenance hemodialysis or peritoneal dialysis during the study, their data after the start of dialysis will be excluded from summary statistics and will be included in listings only.

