9.5 Safety Analysis

Safety variables will include:

- All AEs
- SAEs
- Clinical laboratory test results
- Vital signs

- ECG
- Deaths
- Reasons for dosing interruption or discontinuation
- Laboratory safety summaries will include:
 - Incidence of potassium (1) < 3.0 mEq/L, (2) < 3.5 mEq/L, (3) ≥ 5.1 mEq/L and (4) ≥ 5.5 mEq/L (measured by central laboratory)
 - Incidence of serum magnesium (1) < 1.4 mg/dL (< 0.58 mmol/L), (2) < 1.2 mg/dL (< 0.49 mmol/L) and (3) < 1.0 mg/dL (< 0.41 mmol/L) (central laboratory)
 - Calcium levels, phosphate levels, and serum fluoride levels will be assessed based on central laboratory analysis of samples collected at each of the scheduled study visits

The analysis of treatment-emergent AEs will include all events with onset or worsening on or after the date of first dose of patiomer.

Complete details of the safety analyses will be presented in the SAP.

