4.2 Safety Population

The safety population will include all subjects who have taken at least one dose of patiromer.

The safety population and efficacy population are same in this study, so all analyses will be displayed with one population, i.e. safety population.

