7.10 Safety Analyses

7.10.1 Adverse Events

AEs and SAEs will be coded to system organ class (SOC) and preferred term (PT) with the latest available MedDRA. Adverse event analyses will include only treatment-emergent AEs (TEAEs). A TEAE is defined as any AE that newly appeared or worsened in severity following initiation of study drug administration. If the onset date of an AE is missing, the AE will be considered treatment-emergent unless there is evidence to conclude that it is not. AE listings will include all AEs.

The incidence of TEAEs will be summarized by system organ class (SOC), preferred term (PT) and severity. For those TEAEs that occur more than once during the study period, the maximum severity will be used in the summary by severity.

Descriptive statistical summaries (frequencies and percentages) will be provided for the followings:

- Overall summary of number of subjects with: any TEAE; any TEAE related to study drug; any SAE; any SAE related to study drug; any TEAE leading to study drug dose increase, dose reduction, dose interruption; any TEAE leading to study drug discontinuation
- Summary of all TEAEs by SOC, PT and severity
- Summary of TEAEs related to study drug by SOC and PT
- Summaries of TEAEs leading to study drug dose increase, dose reduction, and interruptions by SOC and PT
- Summary of TEAEs leading to early study drug discontinuation by SOC and PT
- Summary of SAEs by SOC, PT, and severity
- Summary of SAEs related to study drug by SOC and PT
- Summaries of TEAEs of special interest (e.g. allergic reactions, gastrointestinal events, renal events)

A listing for all AEs will be provided, including verbatim term, PT, SOC, severity, whether serious, relationship to study drug, onset and end date, action taken, and outcome of event will be provided. A listing of SAEs and TEAEs leading to any study drug modification or discontinuation (increase, reduction, interruption or discontinuation) will also be provided. In addition, listings will be provided for events of special interest.

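### The dialysis exclusion in SAP 7.1 is not limited to efficacy, so followed literally it removes adverse events after dialysis start from the safety tables that SAP 5.2 and 7.10.1 and protocol 9.5 say cover all events from first dose.

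*SAP*

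**What the plan says.** SAP 7.1, under general considerations, first says how all table results are to be displayed. It then says of subjects who transition to maintenance hemodialysis or peritoneal dialysis that "their data after the start of dialysis will be excluded from summary tables and will be included in listings only". Protocol 9.2 has the parallel sentence, "their data after the start of dialysis will be excluded from summary statistics and will be included in listings only", placed directly after the sentence that defines both the efficacy and the safety populations.

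The safety texts set no such cut-off. SAP 5.2 names every treatment-emergent event as a safety variable. SAP 7.10.1 plans frequency tables of all of them by system organ class, preferred term and severity, and states: "A TEAE is defined as any AE that newly appeared or worsened in severity following initiation of study drug administration". Protocol 9.5 says that the analysis of treatment-emergent events "will include all events with onset or worsening on or after the date of first dose" of patiromer. On the denominator, SAP 4.2 says: "The safety population will include all subjects who have taken at least one dose of patiromer".

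Events after dialysis start can arise and be recorded. Protocol 4.4 says: "Continuation of patiromer (including a dose of 0 g/day) may be allowed for patients transitioning to dialysis under the following conditions". Children withdrawn early "will be followed for safety for 2 weeks after receiving the last dose" of patiromer (protocol 4.3). Protocol 8.2.1 says that "AEs, including SAEs, will be collected throughout the study period", up to the last study visit.

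**The concern.** Safety and tolerability is the secondary objective of the study, and the SAP 7.10.1 tables are where its incidence rates will be read. A programmer who applies SAP 7.1 as worded would drop post-dialysis events from the counts and leave the child in the percentage base. The error runs in one direction only, and only in children whose kidney disease has progressed. Renal events are among the examples SAP 7.10.1 gives of events of special interest.

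The rule also sits oddly with the rest of the SAP, which leans towards counting events. A missing relationship is treated as related, missing severity defaults to severe when no other event with the same term can inform it, and a missing onset date is treated as treatment-emergent unless there is evidence against it.

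Removing potassium values after dialysis start is understandable, because protocol 4.4 itself lists the dialysis prescription among the ways to control hyperkalemia. The documents give no reason for removing adverse events.

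**Working it through.** The point rests mainly on comparing texts; the arithmetic only illustrates scale.

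**Step 1. Scope of the exclusion.** SAP 7.1 refers to the subjects' data and to summary tables, with no restriction by endpoint. The phrase allowing exceptions in the preceding sentence qualifies the display by cohort and dose, not the dialysis rule. SAP 7.10.1 does not mention dialysis. So the literal scope includes the adverse event tables.

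**Step 2. Scope of the safety tables.** SAP 5.2 and 7.10.1 call for all treatment-emergent events. Protocol 9.5 calls for all events from first dose onward. None ends at dialysis.

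**Step 3. Does precedence resolve it?** Protocol section 9 and SAP section 1 both say that the SAP prevails. That puts SAP 7.1 above protocol 9.5. It does not settle SAP 7.1 against SAP 5.2 and 7.10.1, which are in the same document.

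**Step 4. Can such events exist?** Yes. They can occur on drug, if patiromer is continued under the conditions in protocol 4.4, or off drug, in the 2 weeks of safety follow-up after the last dose.

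**Step 5. Numerator and denominator.** The safety population is everyone with at least one dose, so the child stays in N. Let k be the number of children whose only event of a given type begins after dialysis start. The table then understates the proportion with that event by k/N.

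Inputs: N = 12 per age group at the recommended starting dose, and N = 36 to 54 in total (SAP 2.3, protocol 9.3). The value of k is not in the documents, so 0, 1 and 2 are assumed.

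| k | N = 12 | N = 36 | N = 54 |
|---|---|---|---|
| 0 | 0 | 0 | 0 |
| 1 | 1/12 = 8.3 points | 1/36 = 2.8 points | 1/54 = 1.9 points |
| 2 | 2/12 = 16.7 points | 2/36 = 5.6 points | 2/54 = 3.7 points |

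With k = 1 and no other child affected, the table shows 0/12 instead of 1/12 (8.3%), or 0/36 instead of 1/36 (2.8%). The event type then does not appear in the table at all.

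The plan gives no figure of its own for this point. Its one design figure, the 73% lower exact bound for 12 successes in 12, reproduces as 0.025^(1/12) = 0.735 and plays no part here.

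**The case against.** The best defence is that the dialysis sentence is an explicit, pre-specified rule in both documents, that protocol 9.5 leaves the details of the safety analysis to the SAP, and that the SAP prevails. On that view a specific rule narrows a general one, and the treatment-emergent definition merely classifies events without saying which enter a table. This deals with protocol 9.5. It does not deal with SAP 5.2 and the summary of all treatment-emergent events in SAP 7.10.1.

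A second defence is that the tables may be meant to describe safety before dialysis, in which case later events fall outside the question and nothing is understated. That would be a legitimate target, but neither document states it. The claim that incidence can only fall therefore applies to incidence over the whole of follow-up.

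Third, the practical effect may be small or absent, and this stands. Maintenance dialysis is excluded at entry, and children expected to need dialysis within 6 to 8 weeks of Day 1 may not be suitable. Patiromer is in most cases to be stopped as soon as feasible, and follow-up is then 2 weeks. In an uncontrolled study of at most 54 children, a few events can be read from listings, although listings give no rates.

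A reader might infer several stronger things that the documents do not support:

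- **That events are hidden.** They are not. SAP 7.10.1 lists all adverse events, SAP 7.10.2 lists deaths (for which no table is planned in any case), and the data monitoring committee reviews adverse events under protocol 8.6.2.
- **That the disposition table loses withdrawals linked to dialysis.** SAP 7.2 expressly summarizes early withdrawals and their reasons.
- **That SAP 5.4 conflicts with SAP 7.1 over the incidence of laboratory values in given ranges.** Its rule on using all available values concerns scheduled versus unscheduled visits, not dialysis.
- **That the primary endpoint is distorted.** Nothing in the documents shows this.

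**Conclusion.** The wording is wrong as it stands and should be corrected before database lock. As written, SAP 7.1 and protocol 9.2 take post-dialysis events out of the adverse event tables, including any that occur on continued patiromer, while the child still counts in the denominator. The SAP elsewhere promises tables of all treatment-emergent events, and its precedence over the protocol does not remove that internal contradiction.

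Confidence is high about the text and low about any material effect. The figure of 8.3 points per affected child in a cohort of 12, or 2.8 points in 36, assumes that the child's only event of that type begins after dialysis start. How many such children there will be cannot be derived from the documents, and none is a possible answer.

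**What to change.** Reword SAP 7.1 so that the dialysis exclusion applies only to the potassium efficacy summaries and the by-visit central laboratory summaries. Add a sentence saying that the tables of treatment-emergent events, serious events and events leading to discontinuation of study drug include all events from first dose, with a row or flag for onset after dialysis start. Align protocol 9.2 at the next amendment; none is needed for this alone, because the SAP takes precedence.

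The cost is a few sentences in the SAP and one row or flag in the adverse event tables. The data are already collected, and clinical management does not change. The downside is that some events related to dialysis rather than to patiromer will appear in the tables; the flag lets the reader identify them.

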7.2 Subject Disposition

The number of subjects screened, subjects enrolled, subjects who received at least one dose of study drug, subjects who completed the Day 14 visit, subjects who completed the Week-26 visit, subjects who withdrew from the study before the Week-26, the primary reasons for early study termination will be summarized.

Listings of data supporting subject disposition and the reason for screening failures will be provided.

7.3 Demographics and Baseline Characteristics

Demographics and baseline characteristics will be summarized for the ITT and safety population.

The summary of demographic information will include age, gender, race and ethnicity. The summary of patient characteristics at baseline will include, weight, height, and BMI. Baseline medical history will include chronic kidney disease and its etiology, whether patient was on peritoneal dialysis, whether patient ever received a renal transplant, whether patient had diabetes mellitus and its type, , heart failure and its type, ejection fraction percentage, baseline serum potassium and eGFR.

Listings of demographics and baseline characteristics will also be provided.

7.4 Medical History

General medical history will be coded in accordance with the latest MedDRA version and will be summarized by body system (or procedure).

A listing of general medical history will be provided.

7.5 Prior and Concomitant Medications

All prior and concomitant medications will be coded using the latest version of the World Health Organization Drug (WHO Drug) dictionary.

Prior medications are defined as medications with start date before the date of first dose of study drug. Concomitant medications are those taken during the study period and are defined as medications with start date on or before the date of last dose of study drug and end date on or after the date of first dose of study drug, or no end date.

Prior and concomitant medications will be separately summarized by ATC2 class and preferred drug name. Additional summaries may be provided for concomitant medications of interest.

Listings of all prior and concomitant medications will be provided.

7.6 Exposure to Study Drug

The actual prescribed dose of patiromer by cohort, starting dose, and study day will be summarized.

A listing for drug exposure will be provided.

7.7 Treatment Compliance

Treatment compliance for each subject will be estimated and listed separately for the 14-day PD/dose finding period and the long-term treatment phase. Dose compliance will be derived from the total dose of study drug taken by a subject divided by the prescribed total dose over the treatment period for the subject, multiplied by 100.

7.8 Protocol Deviations

The number and percentage of patients with important protocol deviations by category of deviation will be summarized. A listing of important protocol deviations will be provided.

7.9 Efficacy Analyses

7.9.1 Primary Efficacy Analysis

Changes from baseline to Day 14 in serum potassium levels from a central laboratory will be summarized using descriptive statistics. Baseline potassium will be the last non-missing central serum potassium value prior to first dose of patiromer. Descriptive statistics include mean, standard deviation, and 95% confidence intervals.

7.9.2 Secondary Efficacy Analysis

Number and proportion of subjects with central serum potassium levels in the range of 3.8 – 5.0 mEq/L at Day 14 (Initial Pharmacodynamic / Dose Finding Phase) and proportion of subjects with central serum potassium levels in the range of 3.8 – 5.0 mEq/L by visit through Month 6 (Long-Term Treatment Phase) will be presented.

Proportions will be provided along with the 95% confidence intervals, obtained using Exact (Clopper-Pearson) method.

Central serum potassium and mean changes in serum potassium at each scheduled visit will be presented graphically. Central and local laboratory potassium values from serum samples will be included in listings.

7.9.3 Additional Subgroup Analyses

The primary and secondary analyses may be performed for the following subgroups:

- Sex (male versus female)
- Age (12 – <18 versus 6 – <12 versus 2 – <6 years)

- Race (white versus non-white)

